1) Abstract of the study

Post-discharge hospital utilization, i.e., readmissions within 30 days of discharge (30d readmissions) and emergency department (ED) visits, are a high-priority quality measure and target for cost reduction. Patients with diabetes are disproportionately over-represented in 30d readmissions, especially among racial minorities and urban populations. We have developed and validated a tool, the Diabetes Early Readmission Risk Indicator (DERRI), to predict 30d readmission risk among diabetes patients, which is a critical prerequisite for targeting limited resources for reducing readmission risk to those most in need. Currently, there are no proven interventions to reduce the risk of 30d readmission specifically among patients with diabetes. This proposal will assess the feasibility and acceptability of a novel, multifactorial intervention, the Diabetes Transition of Hospital Care Program (DiaTOHC or “My Temple Extra Care Service”), designed to reduce post-discharge hospital utilization rates in a pilot randomized controlled trial. The intervention will include inpatient diabetes and discharge education, comprehensive discharge planning and coordination of care, A1c-based adjustment of diabetes therapy, and post-discharge support. Hospitalized patients with diabetes identified as high risk for readmission based on the DERRI will be randomized to the intervention or the control group, which will receive usual care. Such work is highly relevant in the current era of soaring health care costs and national health care reform.

2) Protocol Title

A Pilot Trial to Prevent Hospital Readmission of Patients with Diabetes (NCT03243383)

3) Investigator

[name], MSc

4) Objectives

We have **retrospectively developed and validated a tool to predict the risk of all-cause 30d readmission among patients with diabetes** called the Diabetes Early Readmission Risk Indicator (DERRI).[1] Based on easily obtained clinical and sociodemographic information available prior to the time of discharge, the DERRI accurately stratifies patients by risk of 30d readmission.

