a) Recruitment Methods

We will recruit study subjects as follows:

1. We will review a daily computer-generated admission log of patients admitted to medical-surgical units at TUH who have been ordered for routine glucose testing. This captures most patients with recognized diabetes.
2. We will review the medical chart of patients on the admission log to determine potential eligibility. We request a waiver of consent and HIPAA to identify candidates. We will access only the minimum data needed to obtain this information.
3. We will request permission to approach the potential subject about the study from a physician on the primary team providing hospital care.
4. Study participants will be provided \$50 after 30 days of follow-up has been completed and outcomes have been assessed. Subjects who also provide an in-depth interview after the follow-up period will be given another \$50.

b) Inclusion and Exclusion Criteria

Screening for eligibility will be performed by chart review and brief history of the potential subject.

Inclusion criteria

1. Diabetes, defined by pre-admission use of a diabetes-specific medication and/or documentation of the diagnosis in the medical record.
2. Age 18 years or older at the time of admission
3. Admission to a non-critical care unit

Exclusion Criteria:

1. Female subjects who are pregnant and/or admitted to an obstetric service

Readmission Pilot Trial

2. Binge drinking (5 or more alcoholic drinks for males or 4 or more alcoholic drinks for females on the same day) or drug abuse within 3 months before admission
3. Receiving palliative care during the hospitalization
4. Participation in another readmission risk reduction program
5. Inpatient death
6. Planned or actual transfer to another hospital or subacute facility
7. Discharge to hospice or a long-term care facility
8. Discharge by signing out against medical advice
9. Discharge expected within 12 hours or admission to a short-stay unit
10. Lack of access to a phone
11. Living more than 30 miles away from TUH
12. Mental condition rendering the subject unable to understand the nature, scope, and possible consequences of the study
13. A1c <5.7%
14. Inability to speak English

c) Local Number of Subjects

Up to 300 subjects will be enrolled locally across the following study groups: 60 subjects in the intervention group, 60 in the high-risk control group, and 180 in the low-risk control group.

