We estimate that 25% of screened patients will not meet eligibility criteria, which means that at least 300 patients will be screened.

d) Study Timelines

Subjects will be enrolled during their hospital stay and will participate in the study for 3 months following hospital discharge. The intervention will be delivered during the 4 weeks following discharge. Final assessment for outcomes will be performed at 3 months after discharge. We anticipate enrollment will occur between July and December of 2019. We estimate that primary analyses will be completed by June of 2020.

e) Study Endpoints

The primary outcome will be the number of initial hospital readmissions within 30 days of discharge. Secondary outcomes will also be assessed at 30 days of discharge unless otherwise specified. Secondary outcomes will include:

1. time to first readmission
2. number of emergency department (ED) visits
3. a composite of 30d readmissions and ED visits

Readmission Pilot Trial

4. number of primary care and specialist provider follow-up visits scheduled and attended
5. incidence of medication review or reconciliation post-discharge
6. cost of post-discharge care as a sum of ED visits, readmission, home health services, and outpatient provider visits
7. cost of the intervention
8. subject experience assessed by a brief questionnaire
9. self-monitored blood glucose levels and frequency of testing
10. change in well-being from baseline to 5 weeks after discharge as measured by the World Health Organization Well-Being Index (WHO-5).[43]
11. change in diabetes-related distress at 5 weeks after discharge as measured by the Problem Areas in Diabetes (PAID) scale.[44]
12. change in perceived social support at 5 weeks after discharge as measured by the Multidimensional Scale of Perceived Social Support (MSPSS).[45]
13. change in perceived stress at 5 weeks after discharge as measured by the perceived stress scale (PSS).[46]
14. change in diabetes knowledge at 5 weeks after discharge as measured by the Diabetes Knowledge Test (DKT2).[47]
15. change in A1c level from baseline to 3 months after the index discharge

f) Procedures Involved in the Human Research

After enrollment, subjects will be sorted into 2 groups based on the predicted risk of readmission by the DERRI: high risk and low risk (Figure 1).

[figure not shown]

Figure 1. Allocation of study participants

Low-risk group:

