The **low-risk group** will be followed in a prospective, observational arm of the study. About 5 weeks after hospital discharge, the Temple medical record will be reviewed for the presence of any hospital or ED visits within 30 days after discharge. If no post-discharge acute visits are found, then the subject will be contacted to determine if any hospital or ED visits occurred at another institution.

- The following data will be collected at baseline: sociodemographics, medical history, including HIV, substance abuse, and mental health status, which are likely risk factors for admission, relevant laboratory results, admission diagnoses, well-being (WHO-5), diabetes-related distress (PAID scale), perceived social support (MSPSS), perceived stress (PSS), diabetes knowledge (DKT2), depression screening by the 2-item Patient Health Questionnaire (PHQ-2), [48] and health literacy by the Brief Health Literacy Scale (BHLS). [49, 50] Subjects who score 3 or more on the PHQ-2 will complete the PHQ-9. [51] Subjects with a PHQ-9 score of 5 or more will be referred to their primary care physician (PCP) for evaluation and management of possible depression. [52] For subjects without a PCP, a study physician will begin medical therapy for depression as needed. For subjects newly discovered to be suicidal, psychiatry will be consulted in the hospital.
- The following data will be collected during follow-up: A1c, discharge diagnoses, hospital readmission (date, primary diagnosis), ED visits (date, primary diagnosis) and patient experience according to a brief questionnaire (Appendix Item 3a).

High-risk group:

For the **high-risk group**, there are two phases in the protocol. Phase A is the pilot RCT to explore the feasibility, acceptability, and efficacy of the intervention. Phase B consists of in-depth interviews with intervention participants and research staff to further explore acceptability and effects of the intervention and to refine the protocol for future study. Subjects in the high-risk group will be randomly assigned with a computer-generated randomization scheme 1:1 in randomly permuted blocks of 2, 4, or 6 to receive either the intervention, the Diabetes Transition of Hospital Care (DiaTOHC) Program (“My Temple Extra Care Service”) or usual care (control).

Phase A: RCT of readmission risk reduction intervention

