All data collected by the research team will be considered part of the participant's confidential record. Data collected on paper from research participants will be placed in a locked file cabinet in the GCRC within 24 hours. The destruction date of paper files will be at least 7 years from the termination of the study and will be authorized by the PI. Access to research and confidential records will be limited to clinical investigators and research coordinators.

h) Data Management

Statistical analysis: Distributions of the data will be assessed by descriptive statistical and graphical methods. To assess the randomization procedure, baseline values of all variables will be compared between the intervention and usual care group. Between-group differences for continuous variables will be compared using the Wilcoxon test. Proportions will be compared between groups using the chi-square test or exact tests when expected cell counts are less than 5. The primary outcome of 30d readmission rate will be compared between intervention and control groups with the chi-square test. Point estimates of 30d readmission rates will be obtained and presented with 95% confidence intervals. Time to readmission will be estimated by Kaplan-Meier curve and compared between groups by log-rank test. The composite of 30d readmission and ED visits will be compared by Cox regression model. Continuous secondary outcomes will be compared using Wilcoxon test. Categorical secondary outcomes will be compared using chi-square test. The primary analyses for all outcomes will be performed in the intention-to-treat (ITT) population. Secondary analyses for all outcomes will be performed in a per-protocol population restricted to subjects who complete at least one follow-up phone call. In addition, outcomes will be assessed for differences by the number of follow-up phone calls

Readmission Pilot Trial

completed (dose-response analysis). Lastly, all outcomes will be assessed in the ITT subgroup of subjects with a baseline A1c >7%. Statistical significance will be claimed at an alpha level of 0.05.

Power analysis: The sample size for Phase 2A was based on an expected drop-out and post-enrollment exclusion rate of 25% as well as the capacity of the research team. Because this is a pilot feasibility trial, the study is not powered to detect a difference in outcomes.

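### The primary chi-square test leaves out the DERRI risk score held for every randomised subject; adjusting for it would be a small gain in precision and prespecification, not the correction of an error

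*Protocol*

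**What the plan says.** The statistical analysis paragraph of Protocol section 8 h) states: "The primary outcome of 30d readmission rate will be compared between intervention and control groups with the chi-square test". It names no covariate for any outcome, including the Cox model for the composite of readmission and ED visits. It adds "Statistical significance will be claimed at an alpha level of 0.05", and the power paragraph says "Because this is a pilot feasibility trial, the study is not powered to detect a difference in outcomes".

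Section 8 f) puts the DERRI ahead of allocation: "After enrollment, subjects will be sorted into 2 groups based on the predicted risk of readmission by the DERRI: high risk and low risk". Only the high-risk group is then randomised, "1:1 in randomly permuted blocks of 2, 4, or 6", with no stratification factor stated. Section 4 describes the score as a predictor of all-cause 30-day readmission, which is the primary outcome, and says that "the DERRI accurately stratifies patients by risk of 30d readmission". Section 8 c) sets the numbers: "60 subjects in the intervention group, 60 in the high-risk control group, and 180 in the low-risk control group".

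Section 8 h) also has all baseline variables compared between the arms as a check on the randomisation. It does not say what follows if they differ.

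**The concern.** A baseline score designed to predict the primary outcome, and complete for everyone randomised, is an obvious covariate for the primary comparison. As written, the score is neither balanced by design within the randomised group nor used in the comparison. Two things are at stake.

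- **Precision.** Part of the outcome variation could be explained at no data cost. With 60 per arm, and efficacy among the things Aim 1 explores, a narrower interval has some value.
- **Prespecification.** If the planned baseline comparison shows the arms differing on DERRI, the team must either report a crude result open to challenge or adjust after seeing the data. Naming one covariate in advance avoids that choice.

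This is not a detail merely left for later: the protocol names a specific unadjusted test.

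**Working it through.** **No stated figure to reproduce.** The protocol gives no power, effect size or control rate. Its 60 per arm rests on an expected 25% loss and team capacity; 60 × (1 − 0.25) = 45 per arm remaining, a number the protocol does not itself state.

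**Inputs from the protocol**
- 60 per arm (section 8 c).
- 30-day readmission of 14.4-21.0% among diabetic patients in general (section 5, Significance).
- Alpha 0.05 (section 8 h), taken as two-sided.

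**Assumptions, because the protocol does not give them**
- Overall DERRI C-statistic C of 0.60 to 0.75.
- High-risk group is the top 25% to 50% of predicted risk.
- Logit of predicted risk is normal and well calibrated.

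**Method.** Truncate the risk distribution to the high-risk group. Let m be the mean risk there and SD(p) the spread of individual risk. Then:
- share of variance removed by adjustment: R² = SD(p)² / [m(1 − m)]
- crude SE of the risk difference: √[2m(1 − m)/60]
- adjusted SE: crude SE × √(1 − R²)
- SD of the chance imbalance in mean predicted risk: SD(p) × √(2/60) = crude SE × √R²
- equivalent extra subjects on 120: 120 × R²/(1 − R²)

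**Worked case: C = 0.70, overall rate 21%, top 40%.** Truncation gives m = 0.330, SD(p) = 0.0978 and a within-group C of 0.618.
- R² = 0.0978² / (0.330 × 0.670) = 0.00956/0.2211 = 4.3%
- crude SE = √(2 × 0.2211/60) = 8.58 points; adjusted SE = 8.58 × √0.957, about 8.40 points
- imbalance SD = 9.78 × 0.1826 = 1.79 points, about 0.21 of the crude SE
- extra subjects = 120 × 0.0433/0.9567 = 5.4

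**Range over the assumptions, 60 per arm**

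| Overall C | Variance saved | Imbalance SD (points) | Extra subjects on 120 |
|---|---|---|---|
| 0.60 | 0.6-1.0% | 0.56-0.79 | 0.7-1.2 |
| 0.65 | 1.5-2.5% | 0.97-1.29 | 1.9-3.1 |
| 0.70 | 3.2-4.9% | 1.45-1.86 | 4.0-6.2 |
| 0.75 | 5.6-8.4% | 2.01-2.48 | 7.2-11.0 |

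The crude SE runs from 7.0 to 9.0 points across these cases, so a one-SD imbalance is between √0.006 = 0.08 and √0.084 = 0.29 of an SE. At 45 per arm the imbalance SD is 0.6-2.9 points against an SE of 8.1-10.4.

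**Effect of selecting on the score.** An overall C of 0.70 falls to about 0.60-0.63 among those randomised. With no restriction to the high-risk group, the saving over the same assumptions would have been 1.6-14.4%.

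**Validity and power.** In simulations of 6,000 trials per scenario, the chi-square test had a type I error of 4.8-5.3%. At a 21% overall rate and top 40%, adjustment changed power by −0.1 to +2.0 points; with C = 0.70, a 50% relative reduction and 60 per arm, it rose from 57.1% to 58.3%. For context, a 30% control rate halved to 15% gives the chi-square test about 50% power at 60 per arm and 40% at 45.

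**The case against.** The strongest case against is that nothing here is wrong. A chi-square test in a 1:1 randomised intention-to-treat comparison is valid, and its error rate already allows for chance imbalance. The trial disclaims power, and a point or two of power would change no conclusion. All of that stands, and it limits this to a minor point. It does not remove the point: the protocol fixes the method, the covariate is already in hand, and naming it in advance costs almost nothing.

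A reader might infer more than the protocol supports:

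- **That the crude result is biased.** It is not; an imbalance of the size shown is ordinary sampling variation, which the standard error covers.
- **That the DERRI is discarded after sorting.** Aim 2 validates its predictions prospectively. For the same reason it cannot be called the best available predictor: section 5 says it has been internally validated only, in a retrospective sample.
- **That the gain is 6-10% of variance.** That needs a C of about 0.65-0.69 inside the high-risk group, implying an overall C of roughly 0.73-0.84. The protocol gives no C-statistic for the DERRI.
- **That the pilot's effect estimate will feed a definitive trial.** The protocol says this only of the Phase B interview findings.
- **That a between-arm difference with its interval is missing.** Section 8 h) mentions intervals for the rates, and an SAP may supply the rest.

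**Conclusion.** The point holds as a minor matter of efficiency and prespecification. The primary comparison is unadjusted, the score exists for all randomised subjects, it targets the same outcome, and no stratification on it is stated. The likely saving is about 1-8% of variance (about 1-11 subjects on 120, at most about 2 points of power), and a typical chance imbalance is under a third of a standard error. The size rests on the assumed C-statistic and cut-off, on the general diabetic readmission rate quoted in the background, and on the score being well calibrated in this hospital. If the DERRI performs poorly there, the gain shrinks towards nothing.

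**What to change.** In section 8 h), prespecify a logistic model of 30-day readmission on arm plus DERRI predicted risk, entered as one continuous covariate on the logit scale. Report the standardised (marginal) risk difference with a 95% CI, either as the primary estimate or at least beside the retained chi-square test, and state which is primary. Enter the same covariate in the Cox model for the composite.

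The cost is wording only, with no new data. The small downside is reliance on a one-covariate model in addition to the 2×2 test.

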Adverse events								X
Low-risk group								
Chart review/phone call								X
Psychometric assessments	X							X
Diabetes knowledge	X							X
A1C	X							X
30d endpoints								X

Readmission Pilot Trial

of follow-up appointments, confirming access to medications, and answering questions.

Data collection: The following data will be collected at baseline: A1c, sociodemographics, medical history, including HIV, substance abuse, and mental health status, which are likely risk factors for admission, relevant laboratory results, admission diagnoses, self-reported goals for health and diabetes, well-being (WHO-5), diabetes-related distress (PAID scale), perceived social support (MSPSS), perceived stress (PSS), diabetes knowledge (DKT2), depression screening by the PHQ-2/9, and health literacy by the BHLS (Table 2).

The following data will be collected during follow-up: A1c, discharge diagnoses, hospital readmission (date, primary diagnosis), ED visits (date, primary diagnosis), physician follow-up appointments scheduled and/or attended, post-discharge medication reconciliation (yes/no), cost of post-discharge care, self-monitored blood glucose levels, Nurse Navigator time to deliver the intervention (minutes), well-being (WHO-5), diabetes-related distress (PAID scale), perceived social support (MSPSS), perceived stress (PSS), diabetes knowledge (DKT2), depression (PHQ), and patient experience according to a brief questionnaire (**Appendix Item 3a [usual care] or 3b [intervention]**). These follow-up data will be collected during a phone call about 5 weeks after the index discharge. Baseline and 3-month post-discharge A1c levels will be obtained as part of standard-of-care. A letter reminding patients to do the 3-month blood draw for the A1c test will be sent by mail.

Data will be collected by phone interviews with subjects and review of the electronic medical record (EMR). The Research Specialist will be primarily responsible for screening and recruiting subjects, data collection and data entry.

Phase B: Qualitative evaluation of intervention

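### Six change outcomes with collected baselines are compared by an unadjusted Wilcoxon test; a baseline-adjusted test would usually be more powerful on the same data (minor)

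*Protocol*

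**What the plan says.** Section 8 e) of the protocol (Study Endpoints) lists 15 secondary outcomes. Items 10 to 15 are changes: WHO-5, PAID, MSPSS, PSS and DKT2 at 5 weeks after discharge, and A1c at 3 months, worded as "change in A1c level from baseline to 3 months after the index discharge".

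Section 8 f) (Data collection, Phase A) puts all six in the baseline list. It opens "The following data will be collected at baseline: A1c, sociodemographics, medical history" and goes on to "well-being (WHO-5), diabetes-related distress (PAID scale), perceived social support (MSPSS), perceived stress (PSS), diabetes knowledge (DKT2". The same six measures appear in the follow-up list.

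Section 8 h) (Statistical analysis) sets the test: "Continuous secondary outcomes will be compared using Wilcoxon test". It mentions no baseline covariate. It also states "Statistical significance will be claimed at an alpha level of 0.05", while the power paragraph of the same section says "Because this is a pilot feasibility trial, the study is not powered to detect a difference in outcomes".

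Section 8 c) gives the group sizes as "60 subjects in the intervention group, 60 in the high-risk control group, and 180 in the low-risk control group". The power paragraph expects 25% drop-out and post-enrolment exclusion.

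**The concern.** A change score subtracts the whole baseline value, which is the best use of the baseline only when it predicts follow-up almost one for one. When the correlation is moderate, subtraction adds baseline noise to the comparison. Regressing follow-up on baseline removes only the part that the baseline predicts.

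The trial will hold both measurements for all six outcomes, so the loss is avoidable. The arms are small and significance will be claimed at 0.05. The results are also meant to guide a definitive trial (section 8 f, Phase B). At stake is the precision of six secondary comparisons. The primary outcome, a readmission proportion, is not involved.

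**Working it through.** **Inputs from the protocol.** 60 per randomised arm, 1:1 allocation, 25% loss, alpha 0.05. Analysed per arm: 60 × 0.75 = 45. The protocol states no power, SD or effect size for these outcomes, so there is no figure of its own to reproduce.

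**Assumptions.** Two-sided test, equal SDs at baseline and follow-up, effect 0.2 to 0.5 SD, r from 0.3 to 0.9.

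**Step 1: variance identities (parametric), in units of the outcome variance.**
- Change score: 2(1 − r)
- Follow-up adjusted for baseline: 1 − r²
- Ratio, adjusted to change: (1 − r²) / [2(1 − r)] = (1 + r)/2

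| r | ratio (1 + r)/2 | variance saved |
|---|---|---|
| 0.3 | 0.65 | 35% |
| 0.5 | 0.75 | 25% |
| 0.7 | 0.85 | 15% |
| 0.9 | 0.95 | 5% |

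If the Wilcoxon test were applied to follow-up values instead of changes, the ratio would be 1 − r²: 0.91, 0.75, 0.51 and 0.19 for the same r. Adjustment gains there too.

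**Step 2: simulated power for the rank tests.** The identities describe means, so the rank tests were simulated directly. Wilcoxon is the rank-sum test on change. Rank ANCOVA is Quade's method: regress follow-up ranks on baseline ranks, then compare residuals between arms. Settings: 45 per arm, normal data, 0.5 SD effect, 6,000 trials each. The Monte Carlo error is at most 1.96 × √(0.25/6000) = 1.3 points per figure.

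| r | Wilcoxon on change | rank ANCOVA | gain (points) |
|---|---|---|---|
| 0.4 | 55% | 69% | 14 |
| 0.5 | 63% | 74% | 11 |
| 0.6 | 72% | 80% | 8 |
| 0.7 | 84% | 87% | 3 |
| 0.8 | 95% | 96% | 1 |

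Separate re-runs gave 53 vs 68% at r = 0.4 (15 points), 63.6 vs 75.0% at r = 0.5 (11.4 points) and 84 vs 87% at r = 0.7 (3 points), all within simulation error of the table. For a bounded 0–100 score at r = 0.5 the figures were 60 vs 73%.

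**Step 3: smaller effect.** At 0.3 SD with normal data: 28 vs 35% (r = 0.5), 42 vs 46% (r = 0.7), 59 vs 60% (r = 0.8). The gain falls to 7, 4 and 1 points.

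**Step 4: very high correlation.** At r = 0.9 and 0.5 SD both tests are near 100% and show nothing, so smaller effects are needed.
- Normal, 0.2 SD: Wilcoxon on change 54%, rank ANCOVA 50% (loss 4). A second run gave 53.5 vs 51.0% (loss 2.5).
- Normal, 0.3 SD: 86 vs 84% (loss 2).
- Heavy tails (t with 3 degrees of freedom), 0.2 SD: 80.7 vs 74.8% (loss 5.9).

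For the normal settings at r = 0.9, a Wilcoxon test on the residuals from regressing follow-up on baseline reached 55% and 87%, at least level with Wilcoxon on change. The same held in every other normal setting run with a non-zero effect.

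**Step 5: type I error.** Over five distribution shapes at r = 0.5, 0.7 and 0.8, Wilcoxon on change gave 4.8–5.4% and rank ANCOVA 4.5–5.6%. Both hold the nominal level.

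**Step 6: interval and test.** A robust 95% interval for the adjusted mean difference covered 94.8–96.3%. At 0.5 SD it disagreed with the rank test on significance in 3–7% of runs with normal data, and in up to 24% under strong skew.

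**The case against.** The case against runs as follows. The Wilcoxon test is valid under randomisation. A one-line rule for a class of secondary outcomes is normal protocol detail, and a statistical analysis plan that is not shown could add baseline adjustment. The study disclaims power, these are 6 of 15 secondary outcomes, and the gains shown depend on an assumed effect and an assumed r. Items 10 to 15 are defined as changes, which Wilcoxon tests directly, whereas rank ANCOVA tests baseline-adjusted ranks of follow-up. Finally, rank ANCOVA is not always the better test.

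Much of this stands, and it limits the point to a minor one. It does not remove it: the protocol leaves no gap here but names the unadjusted test, and the baselines are in hand.

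Two stronger readings are tempting. A reader might infer that the planned test is wrong or biased. It is not; its type I error is correct. A reader might also infer from (1 + r)/2 < 1 that rank ANCOVA wins at every r. That identity belongs to the parametric comparison. The simulations show the rank version level at r = 0.8 and behind at r = 0.9.

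**Conclusion.** The point holds as a minor, low-cost improvement. The planned test is valid but usually less powerful than a baseline-adjusted one on the same data. With 45 per arm, a 0.5 SD effect and normal data, the gain is about 15 points of power at r = 0.4, 11 to 12 at r = 0.5, about 3 at r = 0.7 and none worth having at r = 0.8. At r = 0.9, with effects of 0.2 to 0.3 SD, rank ANCOVA loses about 2 to 4 points with normal data and about 6 in the one heavy-tailed setting. Effect sizes, correlations and shapes are all assumptions.

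A reader might wish to extend the criticism to the cost outcome, "cost of post-discharge care as a sum of ED visits, readmission, home health services, and outpatient provider visits", because a rank test does not address mean cost. The protocol gives no unit costs or event rates from which to show that this would mislead, and reporting mean cost is detail an analyst would ordinarily add. That extension is not part of the finding.

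**What to change.** For items 10 to 15, replace the general sentence with one prespecified baseline-adjusted test. Either of these would serve:
- rank ANCOVA of the follow-up value on its own baseline; or
- a Wilcoxon test on the residuals from regressing follow-up on baseline, which avoided the high-r loss in the normal-data runs.

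Report the baseline-adjusted mean difference with a robust or bootstrap 95% confidence interval. Label it descriptive, since it can disagree with the rank test under skew and should not act as a second test. Keep Wilcoxon on change as a sensitivity analysis.

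The cost is a wording change and slightly more analysis work, with no new data. The one downside is the small power loss for rank ANCOVA if r is about 0.9.
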